### Risk minimization (safety precautions and stopping rules)

The following safety measures will be applied in this study in order to minimize the risk for healthy volunteers:

- Careful dose selection
- Shallow dose escalation using a factor 2 for all rising steps
- For safety reasons, Dose Group 3 will be divided into 2 cohorts of 4 subjects each (3 on active drug, 1 on placebo). The dosing of the cohorts will be separated by at least 48h.
- If one dose level was safe and showed acceptable tolerability and if no stopping criterion was met (see Section [3.3.4](#)), the next higher dose will be given, maintaining a time interval of at least 6 days (referring to the first subject of each dose group)
- An extensive safety laboratory will be performed with special focus on full blood exam (see [Flow Chart](#))
- A thorough ECG monitoring including continuous ECG monitoring for at least 15 min pre dose and over 4 hours post dose to cover the anticipated period of highest drug exposure and additional repeated, with frequency indicated in the Flowchart, single 12-lead ECGs over 96 hours for Dose Groups 1 and 2 or over 144 hours for Dose Group 3 following drug administration. Dose escalation would be stopped as soon as at least 2 subjects at one dose level showed relevant QT prolongation (see Section [3.3.4.3](#) for details).
- In this study, blood pressure and heart rate will be closely monitored (see Flow Chart). Dose escalation will be stopped if at least 2 subjects at one dose level show a sustained decrease in systolic blood pressure of  $\geq 20$  mmHg for at least 2 hours after drug administration compared to baseline (Day 1, predose). Orthostatic testing will be performed to detect whether potential hemodynamic effects of BI 1358894 might interfere with daily life activities. Dose escalation will be stopped if orthostatic

Proprietary confidential information © 2019 Boehringer Ingelheim International GmbH or one or more of its affiliated companies

dysregulation (see Section [5.2.2](#) for definition) is observed in more than 1 subject (severe) or more than 3 subjects (moderate) per dose group

- Adequate safety monitoring will be performed (e.g., vital signs including ECGs, safety laboratory tests including hormone parameters, adverse events including Bowdle visual analogue scales).

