### 7.3.4 Safety analyses

Safety will be assessed as defined by the endpoints listed in Section [2.1.2](#) and 2.2.2 based on the treated set (TS). Safety analyses will be descriptive in nature and will be based on BI standards.

For all analyses the treatment actually administered (= treatment at onset) to the subject will be used (any deviations from the randomised treatment will be discussed in the minutes of the Report Planning Meeting).

Treatments will be compared in a descriptive way. The placebo group in the safety evaluation will consist of all subjects treated with placebo, regardless of the dose group in which they were treated. The test treatment groups will be compared to the placebo group in a descriptive way. Tabulations of frequencies/proportions will be used for the evaluation of categorical (qualitative) data, and tabulations of descriptive statistics will be used to analyse continuous (quantitative) data.

Measurements (such as ECGs, vital signs, or laboratory parameters) or AEs will be assigned to treatments (see Section [5.2](#)) based on the actual treatment at the planned time of the measurement or on the recorded time of AE onset (concept of treatment-emergent AEs).

Therefore, measurements planned or AEs recorded prior to intake of trial medication will be assigned to the screening period, those between trial medication intake until the trial termination date will be assigned to the treatment period. These assignments including the corresponding time intervals will be defined in detail in the trial statistical analysis plan (TSAP). Note that AEs occurring after the last per protocol contact but entered before database lock will be reported to Pharmacovigilance only and will not be captured in the trial database.

Additionally, further treatment intervals (called analysing treatments) may be defined in the TSAP in order to provide summary statistics for other than above periods, such as combined treatments, on-treatment totals, or periods without treatment effects (such as screening and post-study intervals).

Adverse events will be coded using the Medical Dictionary for Regulatory Activities (MedDRA). Frequency, severity and causal relationship of AEs will be tabulated by

Proprietary confidential information © 2019 Boehringer Ingelheim International GmbH or one or more of its affiliated companies

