6. GENERAL ANALYSIS DEFINITIONS

6.1 TREATMENTS

It is planned that in total 24 Japanese healthy male subjects participate in this study, according to 3 sequential dose groups comprising 8 subjects per group. Within each dose group, 6 subjects will receive BI 1358894 and 2 will receive placebo.

For details of dosage and formulation see Table 6.1: 1 below.

Table 6.1: 1 Labels for treatments for use in the CTR

Dose group	Treatment		Short label
1-3	P*	Placebo, tablet, qd	Placebo
1	A	BI 1358894, 2*25 mg tablet, po, qd	BI 50mg
2	B	BI 1358894, 1*100 mg tablet, po, qd	BI 100mg
3	D	BI 1358894, 2*100 mg tablet, po, qd	BI 200mg

‘qd’ means here a single drug administration, not a regular drug administration per day.

*: The placebo group in the safety evaluation will consist of all placebo treated subjects, regardless of the dose group in which they were treated.

The following separate study phases will be defined for the analyses of AEs:

- **Screening** (ranging from 0:00h (midnight) on day of informed consent until administration time of study drug (BI or Placebo))
- **On treatment**
 - **BI/Placebo treatment** (separately for each treatment, ranging from the time of administration of BI 1358894 or Placebo until 0:00h (midnight) on the day after trial termination date)

Please note that all AEs reported between start of trial drug administration and the trial termination date will be considered on treatment (i.e. no follow-up period is considered in this trial).

Two types of AE displays will be provided in the report:

A) Section 15.3 and Appendix 16.1.13.1.8 (for ClinicalTrials.gov) of the CTR displays:

In these displays, the on treatment phase will be analysed (labelled with the name of the study treatment (short label)). Screening will not be included in this analysis.

The following totals will be provided in addition:

- a total over all BI treated phases (“**BI Total**”)

- a total over all on treatment phases included in this analysis ("Total on treatment") (Section 15.3 only)

B) Section 15.4 and Appendix 16.1.13.1.8 (except for ClinicalTrials.gov) of the CTR displays:

- Screening
- On treatment (labelled with the name of the study treatment (short label))

In Section 16.1.13.1.8 AE tables, the following totals will be provided in addition:

- a total over all BI treated phases ("BI Total")
- a total over all study phases ("Total")

Tables of vital signs, ECG and laboratory values will present results by the above mentioned on treatment phase.

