6.7 BASELINE, TIME WINDOWS AND CALCULATED VISITS

The baseline value is defined as the last measurement before administration of BI 1358894 or Placebo.

Section 6.1 of the CTP: *Exact times of measurements outside the permitted time windows will be documented. The acceptable time windows for screening and the end of trial examination are provided in the CTP Flow Chart.*

Study measurements and assessments scheduled to occur ‘before’ trial medication administration on Day 1 are to be performed and completed within a 2 h-period prior to the trial drug administration except PK sample. A blank sample for PK will be collected within 3 h before drug administration.

The acceptable deviation from the scheduled time for vital signs, orthostatic testing and ECG will be ± 10 min and laboratory tests will be ± 30 min for the first 4 h after trial drug administration and ± 30 min thereafter.

[...]

Adherence to time windows will be checked via the consistency check listings at the RPM.

Unscheduled measurements of laboratory data or vital signs will be assumed to be repeat measurements of the most recent scheduled measurement (e.g. for follow-up or confirmation of a particular value). Therefore, unscheduled measurements will be assigned to the planned time point of the previous scheduled measurement.

There will be a centralised evaluation of the 12-lead ECG recordings at the time points and for the ECG recordings specified in the [Table 6.7: 1](#) below:

Section 5.2.4.1 of the CTP: *Triple ECGs will be recorded (within 180 sec) at all-time points on Day 1 to Day 3 (48 h) for Dose Groups 1 and 2 or on Day 1 to Day 7 (144h) for Dose Group 3. At all remaining time points, single ECGs will be recorded.*

Table 6.7: 1 Time schedule of 12-lead ECG recordings

Visit	Day	Planned time [hh:mm] (relative to drug administration)	Study phase	Central evaluation
1	-28 to -1		Screening	NA
2	1	-01:00	Baseline	all 3 single ECGs of the triplicate
		00:30		first of three replicate ECG
		01:00		first of three replicate ECG
		01:30		first of three replicate ECG
		02:00		first of three replicate ECG
		03:00		first of three replicate ECG
		04:00		first of three replicate ECG
		05:00		first of three replicate ECG
		06:00		first of three replicate ECG
		08:00	On treatment	first of three replicate ECG
		12:00		first of three replicate ECG
	2	16:00		first of three replicate ECG
		24:00		first of three replicate ECG
		34:00		first of three replicate ECG
	3	48:00		first of three replicate ECG

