7.8.2 Laboratory data

The analyses of laboratory data will be descriptive in nature and will be based on BI standards.

Laboratory data will be analysed qualitatively via comparison of laboratory data to their reference ranges. Values outside the reference range as well as values defined as possible clinically significant will be flagged in the data listings.

Clinically relevant findings in laboratory data will be reported as baseline conditions (at screening) or as AEs (during the trial) if judged clinically relevant by the investigator, and will be analysed as such.

It is the investigator's responsibility to decide whether a lab value is clinically significant abnormal or not (at the RPM at the latest).

Descriptive statistics of laboratory data will be calculated by planned time point based on the worst value of the subject at that planned time point (or assigned to that planned time point).

The mean normalised values and SD over time for all laboratory parameters, except for parameters that are measured at a single time point will be displayed graphically. The time span is from baseline to post examination.

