7.8.3 Vital signs

Descriptive statistics over time including change from baseline will be performed for vital signs (blood pressure and pulse rate), as well as respiratory rate (RR) and orthostatic tests. In the listing the difference from baseline will also be displayed.

Descriptive statistics will be calculated by planned time point based on the last value of the subject at that planned time point (or assigned to that planned time point).

Clinically relevant findings in vital signs will be reported as AEs.

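### SAP 6.7 can give laboratory and vital-sign values taken after dosing the predose planned time (-1:00), and the plan contradicts itself on their study phase

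*SAP*

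**What the plan says.** SAP 6.7 gives the reason for its mapping: "Unscheduled measurements of laboratory data or vital signs will be assumed to be repeat measurements of the most recent scheduled measurement". It follows that "unscheduled measurements will be assigned to the planned time point of the previous scheduled measurement". The section does not mention drug administration as a boundary for this mapping. It separately defines baseline as the last measurement before administration.

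The summary rules then use the mapped time. Laboratory statistics by planned time are "based on the worst value of the subject at that planned time point (or assigned to that planned time point"). Those for vital signs are "based on the last value of the subject at that planned time point (or assigned to that planned time point").

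Two statements bear on study phase:

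- Protocol 7.3.4 assigns measurements to treatment "based on the actual treatment at the planned time of the measurement or on the recorded time of AE onset", so that "measurements planned or AEs recorded prior to intake of trial medication will be assigned to the screening period". SAP 7.8.1 repeats the second of these.
- SAP 6.1 starts the on-treatment phase at the time of administration. It introduces the phases for adverse events and then adds: "Tables of vital signs, ECG and laboratory values will present results by the above mentioned on treatment phase".

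Protocol 7.3.4 leaves the detailed intervals to the SAP. The SAP in turn refers treatment handling to an analysis data set plan that is not among the documents.

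**The concern.** Treating an unscheduled reading as a repeat of the one before it is sensible while both lie on the same side of dosing. A reading taken on drug cannot confirm an untreated value. Where the two straddle dosing, the rule labels a post-dose observation as predose.

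Two things are at stake. First, any summary of the -1:00 time point can contain a value that was not predose. Second, a brief change that has resolved by the next scheduled reading would appear in no post-dose row of the by-time tables, because it carries planned time -1:00. This is a safety and tolerability trial with 6 active subjects per dose, and protocol 4.2.1 notes that hypotension and tachycardia were reported in toxicology studies. An early unscheduled blood pressure is therefore a plausible event.

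**Working it through.** The plan states no figure for this point, so there is nothing to reproduce. The check traces the rule through the schedule and then gives a small illustration.

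**Inputs.** Times are read from the Dose Group 3 flow chart, because the columns of the Dose Group 1 and 2 chart are not reliably aligned in the text copy used. Footnote 13 of both charts confirms a laboratory sample at 4 h on Day 1.

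| Parameter | Last predose time | First post-dose time | Window in which the mapping crosses dosing |
|---|---|---|---|
| Supine vital signs | -1:00 | 0:30 | 0:00 to 0:30 |
| Orthostatic test (if covered) | -1:00 | 3:00 | 0:00 to 3:00 |
| Safety laboratory | -1:00 | 4:00 | 0:00 to 4:00 |

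The orthostatic row is conditional. SAP 6.7 names laboratory data and vital signs, and SAP 7.8.3 mentions orthostatic tests in addition to vital signs, although under that heading.

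**Step 1, planned time.** The assigned time is the latest scheduled time before the reading. A blood pressure at 0:15 goes to -1:00, and so does a laboratory sample at 2:00.

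**Step 2, summary rule.** At -1:00 the 0:15 blood pressure is later than the true predose reading, so the last-value rule always selects it. The 2:00 laboratory value is selected whenever it is worse than the predose value.

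**Step 3, phase.** Protocol 7.3.4 and SAP 7.8.1 go by planned time: -1:00 precedes intake, so the value belongs to screening. SAP 6.1 goes by actual administration: 0:15 follows dosing, so the value is on treatment. Both cannot hold, and SAP 6.7 does not choose between them. Under either reading the planned time is still -1:00.

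**Step 4, what is not reached.**

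- Baseline is the last measurement before administration, so a post-dose value cannot be baseline.
- Adverse events are phased by recorded onset, so the primary endpoint is unaffected.
- Protocol 5.2.4.1 excludes unscheduled ECGs from the interval analysis.
- SAP 7 lists all individual values.

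**Step 5, size (assumed, not trial data).** Shift in a group mean = change in one subject / n, with n = 6 (each active dose; pooled placebo is 3 × 2 = 6).

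- 10 / 6 = 1.7 mmHg
- 20 / 6 = 3.3 mmHg
- 30 / 6 = 5.0 mmHg

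**Step 6, after the fix.** If a value with actual time after dosing cannot take a predose planned time, all three windows in the table become empty.

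**The case against.** The strongest reply is that SAP 6.1 already answers the point: the on-treatment phase starts at actual administration, and the vital-sign and laboratory tables follow that phase. Protocol 7.3.4 expressly leaves the detail to the SAP. This stands as far as it goes, and it means that a move of the value to screening is not established. It does not settle the matter, because SAP 7.8.1 repeats the planned-time wording and SAP 6.1 does not alter the planned time given by SAP 6.7.

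A second reply is that no passage says a -1:00 row will be tabulated apart from baseline. If the first row shown is baseline, the shift in Step 5 does not occur. That is correct, and it is why the shift is stated only for a by-time summary of -1:00.

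A reader might infer that acute drug effects will be understated in the safety results. The documents do not support that. Clinically relevant findings are reported as adverse events, orthostatic hypotension is itself recorded as one, out-of-range laboratory values are flagged in the listings, and a fall that persists is caught at 0:30, 1:00, 1:30 and 2:00. Nor does the protocol's phrase "to cover the anticipated period of highest drug exposure" help: it explains 4 hours of continuous ECG monitoring and does not place peak exposure in the first 30 minutes. Nor can one assume that every early unscheduled sample reflects a suspected reaction, since SAP 6.7 itself gives follow-up and confirmation as examples.

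**Conclusion.** The point holds in a limited form. As written, SAP 6.7 gives a wrong planned time to any unscheduled laboratory or vital-sign value taken between dosing and the first post-dose time point, and the phase of such a value is contradictory across protocol 7.3.4, SAP 7.8.1 and SAP 6.1.

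The windows are 30 minutes for supine vital signs and 4 hours for laboratory values. A further window of 3 hours applies to orthostatic tests in Dose Group 3 if the rule covers them. The consequence stays within descriptive by-time tables, and few values are likely to be involved. The 1.7 to 5.0 mmHg range assumes a change of 10 to 30 mmHg in one of 6 subjects and a tabulated -1:00 row. The protection of baseline assumes that it is derived from actual times, as its definition implies. The analysis data set plan may resolve the phase conflict, but it could not be checked.

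The point is worth correcting because a stated rule gives a wrong result and the correction is cheap.

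**What to change.** Add to SAP 6.7: an unscheduled measurement whose actual time is after drug administration is never assigned to a predose planned time. It belongs to the on-treatment phase by actual time, is shown as a separate unscheduled on-treatment value, and counts in any on-treatment worst-value or out-of-range summary.

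Moving the value forward to the next scheduled time point would not work. A 0:15 blood pressure moved to 0:30 would be superseded by the scheduled 0:30 reading under the last-value rule, and a laboratory sample taken minutes after dosing could end up in the 4:00 row. A limit on the length of the back-assignment interval would not help either, because even a reading at 0:10 crosses dosing.

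Align SAP 6.1, 6.7, 7.8.1, 7.8.2 and 7.8.3 with this rule, and state whether orthostatic tests are covered.

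The cost is one programming condition and one extra row or flag in the tables. No new data are needed.

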7. PLANNED ANALYSIS

The placebo group in the safety evaluation will consist of all placebo treated subjects, regardless of the dose group in which they were treated.

Safety analysis (refer to [Section 7.8](#)) will be performed by and will be presented in Sections 15.1 to 15.4 of the CTR and in Appendix 16.2 and 16.1.13.1.

Inferential statistical analyses of PK endpoints (refer to Section [7.5.2](#)) will also be performed by and will be presented in Section 15.5 of the CTR and in Appendix 16.1.13.3.

Descriptive data analysis of PK parameters and concentrations will be performed by . The individual values of all subjects and descriptive statistics will be presented in Appendix 16.1.13.5 and Section 15.6 of the CTR, respectively.

The format of the listings and tables will follow the standards defined in the BI standards with the exception of those generated for PK-calculations [\(6\)](#).

The individual values of all subjects will be listed, sorted by treatment group, subject number, and visit.

The listings except PK evaluations will be included in Appendix 16.2 of the CTR.

For end-of-text tables, the set of summary statistics for non-PK parameters is:

N	number non-missing observations
Mean	arithmetic mean
SD	standard deviation
Min	minimum
Median	median
Max	maximum

For analyte concentrations, the following descriptive statistics will additionally be calculated:

CV	arithmetic coefficient of variation
gMean	geometric mean
gCV	geometric coefficient of variation

For PK parameters, the following descriptive statistics will additionally be calculated:

CV	arithmetic coefficient of variation
gMean	geometric mean
gCV	geometric coefficient of variation
P10	10th percentile
Q1	1st quartile
Q3	3rd quartile
P90	90th percentile

The data format for descriptive statistics of concentrations will be identical with the data format of the respective concentrations. The descriptive statistics of PK parameters will be calculated using the individual values with the number of decimal places as provided by the evaluation program. Then the individual values as well as the descriptive statistics will be reported with three significant digits in the CTR.

Tabulations of frequencies for categorical data will include all possible categories and will display the number of observations in a category, as well as the percentage (%) for each treatment group. Percentages will be rounded to one decimal place and will be based on all subjects in the respective subject set whether they have non-missing values or not. The category 'missing' will be displayed only if there are actually missing values.

Units of variables should be given in the titles or column/row descriptors in square brackets (e.g. [mg]).

Exclusion of PK parameters

The ADS ADPP (PK parameters) contains column variables indicating inclusion/exclusion (APEXC) of a PK parameter and an analysis flag comment (APEXCO). All analyses based on the PKS will include parameters if they are not flagged for exclusion, that is APEXCO is equal to "Included".

Exclusion of PK concentrations

The ADS ADPC (PK concentrations per time-point or per time-interval) contains column variables ACEXC or ACEXCO indicating inclusion/exclusion (ACEXC) of a concentration and an analysis flag comment (ACEXCO). Exclusion of a concentration depends on the analysis flag comment ACEXCO. For example, if ACEXCO is set to 'ALL CALC', the value will be excluded for all types of analyses based on concentrations. If ACEXCO is set to 'DESC STATS', the value will be excluded from descriptive evaluations per planned time point/time interval. If ACEXCO contains the addition 'TIME VIOLATION' or 'TIME DEVIATION', the value can be used for further analyses based on actual times. If ACEXCO is set to 'HALF LIFE', the value will be excluded from half-life calculation (and, as a consequence, any calculation that relies on λ_z) only; the value is included for all other analyses.

Further details are given in 001-MCS-36-472_RD-01 "Noncompartmental Pharmacokinetic / Pharmacodynamic Analyses of Clinical Studies" (4) and 001-MCS-36-472_RD-03 "Description of Analytical Transfer Files and PK/PD Data Files" (5).

